7.2 Baseline Visit

Baseline evaluations determine if the participant is an eligible candidate for study participation and establish the participant's health status at the time of study entry. Standard-of-care laboratory evaluations or procedures done prior to signing consent will qualify for these baseline evaluations (i.e. physical exams, routine labs, vital signs) if they have been conducted within 30 days prior to study randomization. All baseline evaluations must be completed before a participant is randomized and study agent is dispensed. If a study participant is found to be ineligible, any blood, urine or tissue samples collected for pharmacokinetics or biomarker assessment will be destroyed. The destruction of the blood, urine or tissue samples collected for these evaluations will be clearly documented in the participant's study records.

7.2.1 Informed Consent

At the Baseline visit, written informed consent will be obtained for all potential study participants prior to conducting any research procedures.

- To properly document that informed consent was obtained, the date and time the informed consent was obtained will be documented in the participant's study records.
- A copy of the signed informed consent will be provided to the participant.
- The Registration Source Documents will be sent to the CLO within one business day of obtaining informed consent from any potential study participant, whether or not they are found to be eligible for the study.

7.2.2 Study Registration

Once a participant has signed a consent form, he is assigned a participant ID (PID) number and is considered registered to the study. PID numbers are assigned sequentially and designate the recruitment site, the study and the participant. The CLO will provide each PO with a Participant Identification Number Log at the time of study initiation. Once a participant is registered, the CLO will be notified immediately, to ensure timely and accurate tracking of accrual. [contact]) or e-mail ([contact]) a copy of the Baseline Visit Guide and the Eligibility Questionnaire to the CLO.

If a consented participant is deemed ineligible (a screen failure), the following documents (provided to PO's at study initiation) must be completed and submitted to the CLO:

- the Baseline Visit Guide
- the Eligibility Questionnaire
- a de-identified copy of the participant's informed consent form
- an Off Study Form
- a Verification Form
- an Adverse Event Tracking Worksheet. If the participant has not experienced an adverse event during the screening process or as a result of baseline study visit procedures, check the box at the top of the page.

Participants will be registered in the OnCore database by CLO staff.

7.2.3 Medical/Surgical History

Complete medical and surgical histories will be obtained.

7.2.4 Physical Exam

The physical exam will include a general physical assessment; vital signs: blood pressure, temperature, heart rate, and respiratory rate (to be taken after the participant has been in a seated position for 5 minutes); height; weight; and ECOG performance status.

7.2.5 Clinical Safety/Eligibility Laboratory Tests

The following clinical laboratory tests will be performed within 30 days prior to randomization: WBC, hemoglobin, platelets, alkaline phosphatase, ALT, AST, total bilirubin, serum creatinine, sodium, potassium, chloride, bicarbonate and total serum PSA.

7.2.6 Concomitant Medications

Document all prescription and over-the-counter medications; herbal remedies; vitamins and supplements the participant is currently taking. The medication name; date reported; dosing regimen; indication; start (at minimum the estimated start year) and stop dates; will be recorded.

7.2.7 Baseline Symptoms

Any current/active signs and symptoms experienced by the participant will be documented as Baseline Symptoms. This will include any abnormal laboratory values that are deemed clinically significant. A baseline symptom that increases in grade during the course of the study will be documented as an adverse event. The AE onset date is the date on which the increase in severity occurred.

7.2.8 Review of Previous Prostate Biopsy Pathology Report

The participant must have had a prostate biopsy performed within 13 months prior to randomization. This will be the pre-study, baseline biopsy. The Gleason score as reported on the baseline biopsy pathology report will be used to determine eligibility. The pathology report will be submitted to the CLO to determine tumor volume for stratification (see Section 3: Study design).

7.2.9 Collection of Blood and Urine for Research Purposes

Supplies for the collection of research blood and urine samples will be supplied by the University of Wisconsin's CP Lab in a research lab kit. Two 3ml red top tubes and two 10ml green top tubes of blood will be collected in addition to the blood drawn for clinical safety/eligibility labs. In addition, a minimum of 10ml of urine will be collected in a urine collection cup. The cup is not provided in the research lab kit. Instructions for collection, handling and shipping of research blood and urine samples are in sections 10.2 and 10.3 of this protocol.

7.2.10 Eligibility Assessment

The Eligibility Questionnaire, provided by the CLO as part of the Visit Guides for this protocol, will be completed, signed, and submitted to the CLO along with the Baseline Visit Guide, clinical laboratory results, the pathology report from the pre-study baseline prostate biopsy, and a de-identified copy of the participant's informed consent form for review and approval prior to randomization.

7.2.11 Randomization

If the participant is deemed eligible, he may be randomized, per Section 6.8 of the protocol.

7.2.12 Drug Dispensing and Compliance Instructions

Participants will be instructed on the importance of compliance with the study agent dosing instructions (section 5) Participants will be provided with a pill diary and instructed to document daily the date and time they take their dose of study agent, indicate the reason for any missed doses, document any lost capsules of study agent, list any side effects or symptoms noticed, list any new concomitant medications taken and indication for that medication and note any additional information they feel is relevant. The participant will be instructed to initial each day's entry.

All bottles of study agent dispensed to the participant must be accounted for by the PO. Participants will be instructed to return all bottles of study agent (empty, full, or partially full) and all unused capsules of study agent that were previously dispensed to them at their next study visit.

No study agent bottles should be discarded by the participant or by study staff. Returned bottles of study agent will be maintained at the site for review by a study monitor and return to the drug repository (MRIGlobal).

7.3 During Study Intervention

7.3.1 At the week 13 and week 39 study visits the following evaluations will be performed: Safety labs and total serum PSA; vital signs and weight; adverse events assessment; review of concomitant medications; compliance assessment; collection of blood and urine for research purposes (plasma and urine pharmacokinetics and serum and plasma biomarkers). The participant will be instructed to delay his dose of study agent on the day of this visit until AFTER blood and urine samples have been collected to allow for a 24-hour post dose pharmacokinetic assessment.

7.3.1.1 Clinical Safety Laboratory Tests

The following clinical laboratory tests will be performed: WBC, hemoglobin, platelets, alkaline phosphatase, ALT, AST, total bilirubin, serum creatinine, sodium, potassium, chloride, bicarbonate and total serum PSA.

7.3.1.2 Vital Signs and Weight

Vital signs (blood pressure, temperature, heart rate, and respiratory rate) will be assessed after the participant has been in a seated position for 5 minutes. The participant's weight will be recorded.

7.3.1.3 Adverse Event Assessment

The participant will be asked about any symptoms or events he has experienced since initiating study therapy. For each event document a verbatim description of the event, date reported, onset and end dates, CTCAE v4 term and severity grade, the action taken, outcome, whether the event was a Serious Adverse Event or not, whether the participant dropped from the study due to the event and the MD's assessment of attribution of the event to the study agent. Any clinical laboratory results that the M.D. deems clinically significant should be documented as an Adverse Event.

7.3.1.4 Concomitant Medications

The concomitant medication list will be reviewed with the participant. Any new prescription, over-the-counter, herbal remedies, vitamins and supplements the participant has taken will be added to the list. The drug name, indication, dosing regimen date reported, start date (at minimum the estimated start year) will be recorded, and new entries will be initialed and dated.

Any changes to the dosing regimen for medications on the list will be documented as well as stop dates for any medications that the participant is no longer taking.

7.3.1.5 Compliance Assessment

The participant's compliance with study agent dosing will be assessed at each visit. The compliance rate is determined using the following calculation: $\frac{\text{The number of capsules dispensed} - \text{the number of capsules returned}}{\text{the number of capsules taken in a period}} = \text{the number of capsules taken in a period} \div \text{the number of capsules prescribed for that period} \times 100 = \% \text{ compliance}$. The pill diary will be reviewed with the participant to ensure that any missed doses and the reason for the missed dose is documented. A participant must have $\geq 80\%$ compliance to be evaluable for this study. If the participant is having issues with compliance, the importance of taking study agent as prescribed and strategies to improve compliance will be discussed with the participant and documented in the visit notes.

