3. SUMMARY OF STUDY PLAN

Study Design

Eligible individuals must be at least 21 years of age or older, with a low-grade, clinically localized prostate cancer. Individuals must have had a prostate biopsy within 13 months of study entry. Use of 5 α reductase inhibitors is prohibited during the study, and for six months prior to the baseline study visit.

Thirty participants will be accrued to this study. Participants will be stratified by tumor volume (≤ 2 positive cores and $\leq 10\%$ of any biopsy core volume is adenocarcinoma vs. >2 positive cores or $> 10\%$ of any biopsy core volume is adenocarcinoma). We expect an enrollment duration of 12-18 months. Participants will be randomized, in a 1:1 ratio, to one of two treatment groups:

PFE (as POMx™) 1000mg (i.e., one (1) 1000mg capsule) taken each morning, by mouth, for 52 weeks ± 1 week

Placebo (0mg PFE) one (1) capsule taken each morning, by mouth, for 52 weeks ± 1 week

Following the baseline visit, participants will return for evaluation at 13, 26, 39 and 52 weeks. Scheduled evaluations/procedures are as follows:

- **Baseline Visit:** Eligibility, safety labs and total PSA (to be processed at the PO's clinical lab). Medical history, physical exam, review of concomitant medications and baseline symptom assessment. Blood and urine collection for research purposes (to be batch shipped when a participant completes the study for analysis by the CP lab at UWI. Analysis will include total serum PSA for doubling time, serum testosterone, plasma pharmacokinetics, plasma biomarkers, and urine pharmacokinetics). Review of the pre-study biopsy clinical pathology report for verification of the presence of adenocarcinoma, confirmation that the Gleason grade meets study eligibility criteria, and for stratification by tumor volume. Participants will be stratified by tumor volume and randomized to one of the two treatment groups.
- **Week 13 and 39 Visits:** Safety labs and total PSA (to be processed at the PO's clinical lab), review of adverse events and concomitant medications, pill count and compliance review, blood and urine collection for research purposes (batch shipped to the CP lab at UWI for analysis of total serum PSA, plasma pharmacokinetics and biomarkers and urine pharmacokinetics).

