5.2 Study Drug Administration

Drug will be dispensed by investigational pharmacists or appropriate study staff at the participating organizations and self-administered by the participants. Participants will take one capsule per day, in the morning, by mouth. Study medication may be taken with or without food.

To ensure that study subjects have access to study drug in case of delayed study visit, they will be dispensed four (4) bottles (120 capsules) of study agent at each visit. Tear-off labels will be utilized for unblinding purposes.

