5.7 Adherence/Compliance

- 5.7.1 Ideally, participants will receive 52 ± 1 weeks of treatment. The required compliance rate for evaluability is $\geq 80\%$. Doses that are missed due to drug holidays (as described in Section 5.6) will not count as non-compliance.
- 5.7.2 The participant's compliance will be measured by evaluating study calendars and pill counts. Participants will be informed, both verbally and in writing at all visits of the following important compliance points:
- Bring all bottles of study drug (whether or not there is medication in the bottle) to study visits.
 - Bring completed pill diary to study visits.

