6.6 Packaging and Labels

Study drug (1,000mg PFE/capsule or placebo) will be packaged in standard 100 CC white, pharmaceutical-grade, sealed bottles containing 30 capsules each. DCP will affix a label on each of the bottles; the randomization code will be printed on the label.

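### The compliance formula in Section 7.3.1.5 counts lost or unreturned capsules as taken, which can overstate the compliance endpoint and the 80% evaluability label

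*Combined protocol and SAP*

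**What the plan says.** Section 7.3.1.5 introduces the rule with "The compliance rate is determined using the following calculation". The layout of the formula is damaged in the text available, but only one reading makes sense: capsules dispensed less "the number of capsules returned" gives capsules taken, and this is divided by capsules prescribed for the period and multiplied by 100. There is no term for lost capsules, no rule for a missing bottle and no upper limit.

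The surrounding provisions are these:

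- **Supply.** Section 5.2 says of participants that "they will be dispensed four (4) bottles (120 capsules) of study agent at each visit", as a reserve against delayed visits. Section 6.6 describes "sealed bottles containing 30 capsules each".
- **Dosing and visits.** Section 5.2: "Participants will take one capsule per day, in the morning, by mouth". Section 3: "participants will return for evaluation at 13, 26, 39 and 52 weeks".
- **Diary.** Section 7.2.12 tells participants to "document any lost capsules of study agent" and to note missed doses with reasons. Section 7.3.1.5 has staff review the diary so that missed doses and reasons are on record, but does not link that review to the rate.
- **Sources.** Section 5.7.2 bases compliance on study calendars and pill counts together. Section 13.6 mentions pill counts only.
- **Use.** Section 5.7.1: "The required compliance rate for evaluability is" at least 80%. Compliance is secondary objective 1.2.1, and Section 13.5 compares the arms on missed pills with a Wilcoxon rank-sum test. Section 13.6 says compliance is not used for the primary analysis.

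**The concern.** A pill count measures what did not come back, which equals what was taken only if nothing was lost or left at home. The protocol foresees losses, since it asks for them in the diary, but then computes the rate as if there were none. Within a period, a loss can only raise the rate.

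At stake is a secondary endpoint. If the missed pills in Section 13.5 come from this count, they are understated and can even be negative. The same rate decides who is labelled evaluable, so a man well below 80% can be labelled as above it.

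**Working it through.** **Inputs.** Bottles per visit: 4 (5.2). Capsules per bottle: 30 (6.6). Dose: one capsule a day (5.2). Visits every 13 weeks (3). Threshold: 80% (5.7.1, 7.3.1.5).

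**The plan's own figure.** 4 × 30 = 120 capsules per visit, as Section 5.2 states.

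**Nominal period.** 13 × 7 = 91 capsules prescribed. A man who misses nothing should return 120 − 91 = 29.

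**Formulas.**

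- Rate as stated = (dispensed − returned) / prescribed × 100.
- True rate = taken / prescribed × 100.
- As dispensed = taken + returned + lost, the stated rate exceeds the true rate by lost / prescribed × 100.

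**One 91-day period, 120 dispensed.**

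| Taken | Lost | Returned | True rate | Stated rate |
|---|---|---|---|---|
| 91 | 0 | 29 | 100.0% | 100.0% |
| 60 | 30 | 30 | 65.9% | 98.9% |
| 60 | 13 | 47 | 65.9% | 80.2% |
| 70 | 3 | 47 | 76.9% | 80.2% |
| 91 | 29 | 0 | 100.0% | 131.9% |

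- A full lost bottle adds 30/91 = 33.0 points in that period.
- To reach 80% a man needs 0.80 × 91 = 72.8, so 73 capsules. With 60 taken, 73 − 60 = 13 lost capsules suffice.
- The ceiling is 120/91 = 131.9%.
- In the second row the count implies 91 − 90 = 1 missed pill, where 91 − 60 = 31 were missed. In the last row it implies 91 − 120 = −29.

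**Visit windows.** With both visits at opposite ends of their ±1 week windows, the interval runs from 77 to 105 days. With 60 taken and 30 lost, the rate moves from 60/77 = 77.9% to 90/77 = 116.9%, or from 60/105 = 57.1% to 90/105 = 85.7%.

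**Whole study.** 52 × 7 = 364 doses. One full lost bottle adds 30/364 = 8.2 points. A man scored at 292/364 = 80.2% may have taken 262/364 = 72.0%. A man who takes 60 in one period, 91 in each of the other three and loses one bottle scores (90 + 273)/364 = 99.7% against a true (60 + 273)/364 = 91.5%. He is above 80% either way.

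**Role of the spare capsules.** With exactly 91 dispensed, 61 taken and 30 lost, the stated rate is 91/91 = 100% against a true 61/91 = 67.0%. The spare stock does not create the error. It lets the rate pass 100%, and it lets a man lose capsules without running out.

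**The case against.** The strongest reply is that little depends on the rate and that other controls would expose a loss.

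- **Primary analysis.** Section 13.6 keeps compliance out of it and excludes only random dropouts and men who never took treatment. Section 13.8 likewise includes all eligible men who received agent. A man wrongly labelled as above 80% is analysed either way. This stands. A reader might infer that the IGF-1 comparison is biased by this formula, and the documents do not support that.
- **Other controls.** Section 7.2.12 requires sites to account for every bottle, Section 6.5 requires dispensing and return records, and Section 5.7.2 names calendars as well as counts. A missing bottle should be noticed, but none of these provisions changes the computed rate. The Visit Guides and the Data Management Plan may say more; they are not available here.
- **The endpoint is missed pills, not a percentage.** True, and the diary records missed doses. But Section 13.5 names no source, and the only one Section 13.6 names is the pill count.
- **Late returns.** A bottle left at home and brought to the next visit may offset the earlier excess, so the bias need not persist over the year. The text does not say how such a bottle is credited. A capsule that is truly lost is never corrected.

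Other stronger readings also fail. An unreturned bottle adds only the capsules left in it, and an empty one adds nothing. Adding a full bottle to 91 doses would give 121/91 = 133.0%, but only 120 capsules are issued. The documents give no loss rate, so they do not show that a forgotten bottle is common, nor any reason for losses to differ between blinded arms. Nor do they tie the feasibility objective (1.2.7) to a compliance threshold, so an over-favourable feasibility conclusion does not follow. Exposure has separate evidence in the plasma and urine metabolites collected at every visit.

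**Conclusion.** The concern holds in limited form. As written, the rule gives a wrong compliance figure whenever capsules are lost or not returned, and the wrong figure is too high for that period. The size is 33.0 points for a full bottle in one nominal 13-week period and 8.2 points over 364 days. The documents do not say whether the 80% criterion applies by period or to the whole year, so both figures are needed.

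The effect is limited to the compliance endpoint (1.2.1, 13.5) and the 80% label. This is worth correcting before analysis, but it does not threaten the primary result. The examples assume one capsule a day at full dose and loss amounts chosen for illustration. The point about missed pills assumes that they are derived from the count.

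**What to change.** In Section 7.3.1.5, define capsules taken as dispensed, minus returned, minus capsules recorded as lost in the diary. Where a bottle is not returned, or the result exceeds 100%, use the diary count of doses taken for that period. Use this one figure for the 80% label and, through the missed pills it implies, for the comparison in Section 13.5. In the same edit, state the period over which the 80% criterion is applied.

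The cost is a short change to Section 7.3.1.5 with a matching line in the Visit Guide. No visit, form or data item is added. Some reported compliance rates will fall, and the result will depend partly on self-reported diary entries.

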7.3.1.6 Collection of Blood and Urine for Research Purposes

In addition to the blood drawn for clinical safety labs, one 3ml red top tube and two 10ml green top tubes of blood will be collected for research assays using the supplies provided in the research lab kit. A minimum of 10ml of urine will be collected in a urine collection cup. The cup is not provided in the research lab kit. Instructions for collection, handling and shipping of research blood and urine samples are in sections 10.2 and 10.3 of this protocol.

7.3.2 The 26-week visit is identical to the week 13 and 39 visits (as described in section 7.3.1) with the exception of the following two additional evaluations:

7.3.2.1 Physical Exam

The physical exam will include a general overall physical assessment as well as a standard of care prostate examination by a study doctor.

7.3.2.2 Collection of Blood and Urine for Research Purposes

In addition to the blood drawn for clinical safety labs, two 3ml red top tubes and two 10ml green top tubes of blood will be collected for research assays using the supplies provided in the research lab kit. A minimum of 10ml of urine will be collected in a urine collection cup. The cup is not provided in the research lab kit. Instructions for collection, handling and shipping of research blood and urine samples are in sections 10.2 and 10.3 of this protocol.

7.4 Evaluations at Completion of Study Intervention (Week 52±1W or end of study therapy)

The Week 52 Visit (or end-of-study therapy visit, whichever comes first) is identical to the week 13 and 39 visits as described in section 7.3.1 with the following additional evaluations:

- a physical exam
- collection of a second 3ml red top tube for research biomarker assessment
- a prostate biopsy

As for the previous visits, the participant will be instructed to delay his dose of study agent on the day of this visit until AFTER blood and urine samples have been collected to allow for a 24-hour post dose pharmacokinetic assessment. **However, the participant WILL be instructed to take his final dose of study agent immediately following the collection of the research blood and urine samples and prior to the prostate biopsy to allow for the assessment of study agent levels in prostate tissue.**

